- 1. Describe the change in symptom burden in sub-acute (Part A) and acute (Part B) concussion for the two groups.** This aim defines our primary objective. In Part A we will enroll a maximum of 30 subjects in the open-label treatment Arm (OXE-103) but will stop recruiting when that arm has 20 participants who have completed study requirements. All Part A participants must be diagnosed with a concussion and experience persistent concussion symptoms \leq 28 days post injury. The Part A non-treatment concurrent control Arm will enroll a minimum 20 participants who complete the study requirements, but may continue to recruit more than 20 participants while the Part A open-label treatment Arm is still recruiting. In Part B we will enroll a maximum of 50 subjects but will stop recruiting after each arm (OXE-103 Arm and placebo Arm) has 20 participants who have completed the study requirements. In Part A subjects will receive OXE-103 open-label and in Part B we will randomize 1:1 to placebo versus OXE-103. The Post-Concussion Symptom Score questionnaire (PCSS) will be used as an overall measure of symptom burden. The number of symptoms and severity at each time point are also measures of interest. In addition, subjects will be asked to identify and rank the 4 most bothersome symptoms. We hypothesize that changes in these most bothersome symptoms may have a higher correlation to improvement in quality of life. A visual comparison of change in the two groups will be made. We will consider a change of 20% to be clinically meaningful. Our primary aim will describe the change in symptoms between day 1 and day 15.
- 2. Describe the change in quality of life between the two groups.** This aim defines one of our secondary objectives. To assess this, we will administer the Quality of Life after Brain Injury scale (QOLIBRI) and a Patient Global Assessment of Status (PGAS). A change of 20% will be considered clinically meaningful. Our primary objective with this aim will assess the change between days 1 and 15.
- 3. Describe the correlation between the change in symptom burden and quality of life.** This is an exploratory aim. We hypothesize that improvement in symptom burden will correlate with improvement in quality of life measures. This may be more evident in the correlation between the change in the 4 most bother symptoms and quality of life measures. This aim will describe this correlation between days 1 and 15.

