5.1 Primary Efficacy Outcome Measures

- PCSS severity responder as defined by $\geq 20\%$ improvement over baseline at Day 15 in the severity score
- PCSS symptom responder as defined by $\geq 20\%$ improvement over baseline at Day 15 in the number of symptoms
- PCSS 4MBS responder as defined by $\geq 20\%$ improvement over baseline at Day 15 in the 4MBS severity score
- Change from baseline in PCSS severity score at each post-baseline assessment (Days 4, 8, 11, 15, 21 and 44)
- Change from baseline in PCSS number of symptoms at each post-baseline assessment (Days 4, 8, 11, 15, 21 and 44)
- Change from baseline in PCSS 4MBS severity score at each post-baseline assessment (Days 4, 8, 11, 15, 21 and 44)

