6.1 General Methods

This pilot study will describe changes observed in the two treatment groups, placebo versus OXE-103, separately for each part. Since the study is exploratory, analyses will focus on descriptive comparative statistics and not on a pre-specified statistically significant primary endpoint. Data will be used to enable power calculations and the definition of suitable clinical endpoints for further clinical development. Data from baseline and on Study Days 4, 8, 11, 15, 21, and 44 will be analyzed. Note that day definitions in this study will follow the Clinical Data Interchange Standards Consortium in that there is no Day 0;

assessments performed prior to randomization will be done on Days -7 and -3 (Part A only) and randomization is considered Day 1.

For all evaluations of changes from baseline, baseline is defined as the last reported value before the first dose of study drug. In most instances, this will be the value recorded on Day 1.

For the evaluation of safety, a treatment-emergent finding is any result that is newly reported after the first dose of study drug. This may include an existing condition which worsens in severity after the start of treatment.

Continuous variables such as total score or change from baseline will be summarized by the number of observations, mean, standard deviation, median, minimum and maximum value. Graphs of changes from baseline over time will present the means and 95% confidence intervals.

Binary or categorical variables will be summarized by the number of observations in each category along with the percent of observations.

To aid in interpretation of the importance of relationships, correlation coefficients (Pearson and Spearman) will be reported with p-values.

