6.8 Efficacy Analysis

As described previously, binary variables (responders) and continuous variables (values and changes from baseline) will be summarized with appropriate descriptive statistics for each treatment group and each visit (as needed). Changes from baseline over time will also be presented graphically with means (95% confidence intervals) with both treatment groups presented on the same figure.

To evaluate the appropriateness of the current responder definitions, a Receiver Operating Characteristic (ROC) analysis will be performed for each response outcome measure. The current definitions indicate that a ≥20% improvement over baseline is required for a subject to be considered a responder. In the ROC analysis, the percent improvement will be varied from 5% to 95% to determine which percentage is best for distinguishing OXE-103 treated subjects from placebo subjects. If data suggest an early treatment response, the ROC analysis may be performed for a time point earlier than Day 15.

FDA pre-IND guidance from the FDA on the clinical development of OXE-103 advised that “***The outcome measure should be constructed in a way that ensures that a score change is indicative of a meaningful improvement in how a patient feels or functions that comes from a treatment effect specific to mild TBI.***” Pearson and Spearman correlation coefficients (and p-values) will be calculated to examine

relationships between the PCSS changes and changes in the quality of life measures (QOLIBRI total score and PGAS VAS).

Relationships between PCSS changes and changes in cognition and balance (BrainCheck composite measure) will also be examined using correlation coefficients.

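### SAP 6.8 lets an apparent early treatment response decide the day of the responder ROC analysis, so an ROC run at a day chosen this way is optimistic

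*SAP*

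**What the plan says.** SAP 5.1 defines three responder outcomes: PCSS severity, number of symptoms, and the four most bothersome symptoms. Each is fixed at Day 15; the first requires at least 20% "improvement over baseline at Day 15 in the severity score". Protocol Specific Aim 1 uses the same day: "Our primary aim will describe the change in symptoms between day 1 and day 15".

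SAP 6.8 then adds: "To evaluate the appropriateness of the current responder definitions, a Receiver Operating Characteristic (ROC) analysis will be performed for each response outcome measure". In that analysis "the percent improvement will be varied from 5% to 95% to determine which percentage is best for distinguishing OXE-103 treated subjects" from placebo subjects. The section closes its account of the ROC with: "If data suggest an early treatment response, the ROC analysis may be performed for a time point earlier than Day 15".

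SAP 6.8 does not say what counts as suggesting a response, which earlier days are candidates, or whether the Day 15 ROC is reported as well. PCSS is assessed at Days 4, 8 and 11, so those are the possible days. SAP 6.14 plans no unblinded interim analysis and unblinds each part only after its database is locked. It foresees a blinded data review but does not name that review as the basis for choosing the ROC day. On use of the data, SAP 6.1 says: "Data will be used to enable power calculations and the definition of suitable clinical endpoints for further clinical development".

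**The concern.** A treatment response is naturally judged by comparing the arms, and SAP 6.8 itself puts both arms' mean changes over time on one figure. In blinded Part B that comparison exists only after unblinding, in the data on which the ROC is then run. The rule also works in one direction: the day moves only when an earlier day looks favourable. The largest of several correlated estimates is biased upward, so the AUC and best cut-off at a day chosen for its separation look better than they are.

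This is separate from the search over cut-offs. With the cut-off held at 20%, the day would still be selected on the observed effect. With the day held at Day 15, the cut-off search would still be optimistic.

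At stake is what the pilot hands on. The ROC is meant to judge the responder definition, and the data are meant to inform endpoints and sample sizes. A later trial could adopt an assessment day that stood out by chance, or plan on an inflated separation. Nor would the choice have to be recorded: SAP 1 requires deviations to be documented, but a switch that the SAP permits is not a deviation.

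**Working it through.** The documents give no AUC, alpha, power or effect size, so there is no planned figure to reproduce. The check simulates the rule when there is no drug effect.

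**Inputs from the documents.** 20 completers per group (SAP 4); candidate Days 4, 8, 11 and 15 (SAP 5.1); a default of Day 15 with an optional earlier day (SAP 6.8).

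**Assumptions not in the documents.** Four equally correlated normal day scores with between-day correlation ρ of 0.3 to 0.9; a 60% response rate in both arms for the responder gap; 20,000 simulated trials per setting. As SAP 6.8 states no trigger, two are used:

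- Rule (a), the worst case: always use the day with the largest AUC.
- Rule (b), conditional: stay at Day 15 unless the best earlier AUC beats Day 15 and exceeds 0.5 + 1.645 SE.

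**Formulas.** AUC = U / n², with U the Mann-Whitney statistic for OXE-103 against placebo. Under no effect, SE = √[(2n + 1) / (12n²)] = √[41 / 4800] = 0.092. The threshold in rule (b) is 0.5 + 1.645 × 0.0924 = 0.652.

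**Results with no drug effect (true AUC 0.50, true responder gap 0).** The Day 15 AUC averages 0.50 at every ρ.

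| ρ | Rule (a): mean AUC | Rule (b): trials that move | Rule (b): mean AUC if moved | Rule (b): mean AUC overall |
|---|---|---|---|---|
| 0.3 | 0.581 | 12.7% | 0.691 | 0.520 |
| 0.5 | 0.569 | 11.1% | 0.692 | 0.514 |
| 0.7 | 0.554 | 9.3% | 0.692 | 0.508 |
| 0.9 | 0.533 | 7.1% | 0.693 | 0.504 |

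Under rule (a), the mean responder gap at the AUC-chosen day is about 10 percentage points at ρ = 0.5, ranging from 11 (ρ = 0.3) to 5 (ρ = 0.9).

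**With a real effect, the same on every day** (true AUC 0.584 or 0.638, ρ 0.5 to 0.9), rule (a) still overstates AUC by 0.03 to 0.07. Rule (b) overstates it by 0.09 to 0.13 in the trials that move.

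**The cut-off search on its own.** With the day fixed at Day 15 and no effect, the best-cut-off Youden index still averages about 0.15. Under rule (a) it is 0.18 to 0.23 for ρ from 0.9 down to 0.3. Fixing the day removes the second layer of optimism, not the first.

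**The case against.** The strongest reply is that little can move. The sentence concerns only the ROC. The responder outcomes stay at Day 15, and SAP 6.8 still calls for responder and change summaries by group and, as needed, by visit, with the time course plotted. A reader might infer that the Day 15 answer to the primary objective could be displaced by an earlier result; the documents do not support that.

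Second, the ROC is promised for each response measure, those measures are defined at Day 15, and the earlier analysis only may be performed. It can fairly be read as an addition to Day 15. That stands as a possible reading, but the text does not settle it, and an earlier-day ROC selected on the data is optimistic either way.

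Third, SAP 6.8 does not tell the analyst to take the best of four days. A reader might infer that an earlier day would replace Day 15 about 75% of the time. That figure is just three of four exchangeable days under the worst-case rule. A null responder gap of 13 points might also be inferred, but it arises only if the day is picked by the largest gap; at the AUC-chosen day it is about 10.

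Fourth, the study is declared exploratory and unpowered, and SAP 5.3 openly allows responder rates on other days to be examined. This stands against any claim about type I error, because no formal test is planned. It does not answer the optimism, since informing endpoints and power calculations is the stated use of the data. Nor do the documents say that the ROC day's figures will be the planning input; that remains a risk rather than a stated plan.

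Finally, the current protocol makes Part A open-label against a non-treatment control, so a randomised null comparison of OXE-103 with placebo describes Part B only.

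**Conclusion.** The point holds for the ROC analysis. SAP 6.8 lets its day depend on an observed response, without a criterion and without saying that Day 15 is still shown. A result at a day chosen this way overstates separation. The direction was the same in every scenario examined.

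The size is less certain because the trigger is unstated and the correlation is assumed. Average overstatement of a null AUC runs from under 0.01 to 0.02 with the conditional trigger to between 0.03 and 0.08 in the worst case. It is large, about 0.19, in the minority of null trials (about 7% to 13%) where the conditional trigger moves the day.

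These figures rest on 20 per arm and equally correlated normal scores, and the responder gap also on a 60% response rate. They illustrate optimism in one measure of a randomised comparison, not the error rate of a planned test. The bias would not arise if the day were chosen from blinded pooled data or from external data, but the SAP does not say so. The change should be made; the Day 15 responder results do not depend on it.

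**What to change.** Replace the sentence in SAP 6.8 with: *The ROC analysis will be performed at Day 15 for each response outcome measure. The same analysis will also be performed at Days 4, 8 and 11 regardless of the results, reported together with Day 15, and labelled exploratory; no day will be selected on the observed difference between arms.*

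Add that any earlier-day figure used to plan a later trial is hypothesis-generating. Planning inputs need not be restricted to Day 15, since the pilot is meant to help define endpoints.

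This keeps the sponsor's view of an early response. PCSS is already collected on all four days, so the cost is a short SAP edit and three more runs of the same program per measure. The downside is that the reported figure may look less favourable. The change does not remove the optimism from the cut-off search.

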6.9 Safety Analysis

AEs commonly reported for OXE-103 will be summarized for each treatment group, by study day of assessment and will include an 'At any time' category.

An overview of UU AEs will provide the number (%) of subjects in each treatment group with any TE-AE, TE-SAE, TE-DAE, TE-AE related to study drug,, and TE-AE classified as Grade 2 or higher according to CTCAE, version 5.0. Additionally, TE-AEs, related TE-AEs and Grade 2 or higher TE-AEs will be summarized for each treatment group by Medical Dictionary for Regulatory Activities (MedDRA) system-organ class (SOC) and preferred term (PT) as obtained from CTCAE, version 5.0. In these summaries, a subject may be counted only once for each PT and SOC. Details for any TE-SAEs or TE-DAEs will be provided in individual subject data listings.

Clinical laboratory test, vital sign (including body weight), ECG and PHQ-9 values and changes from baseline will be summarized with appropriate descriptive statistics for each treatment group and each visit.

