In the event that subjects are enrolled by the Trauma team into Part B while having an inpatient status at TUKHS, the study team, Investigational Pharmacy, and the medical team will work together to dispense, store, and administer the study medication. The study team will continue to work with the Investigational Pharmacy and medical team, as appropriate, for the duration of the subject's inpatient status while on study, as necessary to comply with this protocol.

Attrition: This is a pilot study and no previous data exists as a basis to estimate attrition for this study. Any study participant who withdraws consent or is removed from Part A or Part B of the study during the 28-day trial period or does not successfully complete the protocol required 14 days of dosing may be replaced to allow for 40 subjects who complete the protocol.

Target Duration: The target duration of the treatment intervention with OXE-103 will be two weeks. The total involvement in the study including screening and follow up assessments will be 8 weeks.

Adverse Events: Oxeia, the supplier to the study team of the OXE-103 and placebo, performs and submits safety reports to the FDA under a separate IND. As OXE-103 has already undergone safety testing and the safety profile is known, the adverse events associated with OXE-103 are included in an Investigator's Brochure written by Oxeia Biopharmaceuticals. For the purposes of this study, the study team will collect all adverse events reported by subjects including SAEs and TEAEs regardless of suspected causality, and in accordance with appropriate rules and regulations. Study team will report any that are deemed by Investigator to be:

- Unexpected AND related
- Expected but occurring at an increased frequency or severity
- Occurring in such a way that changes the risks/benefit ratio to study participants and warrants an update in consent form and/or protocol.
- All SAE's will be reported per applicable rules and regulations (IRB/FDA)

Depression Screening: The study team will administer the PHQ-9 questionnaire at specified timepoints to help identify any potential risk or need for intervention.

Safety Monitoring: Subjects participating in Part A Arm 2 (non-treatment control) will not require safety monitoring. All other subjects participating in Part A Arm 1 and Part B Arms 1 & 2 will require safety monitoring.

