5.4 Safety Outcome Measures

Any laboratory, vital sign or ECG result meeting Common Terminology Criteria for Adverse Events (CTCAE), version 5.0, will be included in adverse event (AE) reports. Any unexpected findings on physical or neurological examinations will also be included in AE reports.

- Occurrence of any AEs commonly reported for OXE-103, CTCAE Grade 1 (mild) only.
- Occurrence of any unanticipated or unexpected (UU) treatment-emergent (TE) AE, UU serious AE (TE-SAE), UU AE leading to study drug discontinuation (TE-DAE), UU TE-AE related to study drug and UU TE-AE classified as Grade 2 or higher according to CTCAE, version 5.0. [Note that any AE commonly reported for OXE-103 that has CTCAE Grade 2 (moderate) or higher will be included among the UU TE-AEs.]
-
- Change from baseline in clinical laboratory parameters at each post-baseline assessment (Days 8, 15 and 21)
- Change from baseline in vital signs (including body weight) at each post-baseline assessment (Days 8, 15 and 44)
- Change from baseline in ECG intervals at each post-baseline assessment (Days 8, 15, 21)
- Change from baseline in Patient Health Questionnaire (PHQ)-9 total score at each post-baseline assessment (Days 8, 15 and 44)

6. Statistical Methods

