6.3 Subject Accountability

The number of subjects screened will be summarized along with the reasons for screen failure. The number (%) of subjects randomized, treated, completing treatment, completing study and in each analysis set will be summarized by treatment group. Reasons for not completing treatment and/or study will also be summarized by treatment group.

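### The adverse-event overview is limited to 'unanticipated or unexpected' (UU) events, so no planned overview gives the incidence of all, all related or all discontinuation TE-AEs

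*SAP*

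**What the plan says.** SAP 5.4 sets up two classes of adverse event. The first is "Occurrence of any AEs commonly reported for OXE-103, CTCAE Grade 1 (mild) only". The second is the UU class. Any treatment-emergent event, serious events, events leading to discontinuation, related events and events of Grade 2 or higher are defined as outcomes for this second class only. A bracketed note moves more severe common reactions across: "Note that any AE commonly reported for OXE-103 that has CTCAE Grade 2 (moderate) or higher will be included among the UU TE-AEs".

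SAP 6.9 follows the split. The common events get their own table: "AEs commonly reported for OXE-103 will be summarized for each treatment group, by study day of assessment", with a further category for occurrence at any time. The overview is then confined to the other class: "An overview of UU AEs will provide the number (%) of subjects in each treatment group with any TE-AE, TE-SAE, TE-DAE", followed by related events and events of Grade 2 or higher.

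Two later sentences in 6.9 do not repeat the UU limit. One covers the SOC/PT tables: "Additionally, TE-AEs, related TE-AEs and Grade 2 or higher TE-AEs will be summarized for each treatment group". The other covers listings: "Details for any TE-SAEs or TE-DAEs will be provided in individual subject data listings". SAP 6.3 adds: "Reasons for not completing treatment and/or study will also be summarized by treatment group".

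On collection, the Protocol (Adverse Events) says "the study team will collect all adverse events reported by subjects including SAEs and TEAEs regardless of suspected causality". The SAP Introduction gives the SAP precedence over the Protocol where analyses differ.

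**The concern.** SAP 6.1 treats any result newly reported after the first dose as treatment-emergent. A mild common reaction meets that definition, yet it has no place in the overview row for any TE-AE. If the investigator judges it related, it does not count as a related event there. If the subject stops the drug because of it, it does not count as a TE-DAE there.

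The overview is the table most readers take as the safety result. Its row labels read like totals, but they are totals for a subset. The comparison most exposed is Part B, OXE-103 against placebo. It is the only comparison with adverse events collected in both arms, because the Protocol exempts the Part A non-treatment arm from safety monitoring and its schedule has no adverse-event row.

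**Working it through.** The plan states no adverse-event rate and no safety sample size, so there is no figure to reproduce. The check is a reading of 5.4 against 6.9, then set arithmetic.

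**Which overview rows are affected**

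- Any TE-AE, related TE-AE and TE-DAE: incomplete, because Grade 1 common reactions are excluded by class.
- Grade 2 or higher: not affected, since the note in 5.4 brings common reactions of that grade into UU.
- TE-SAE: affected only if a serious event is graded 1, which would be unusual.

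**What the separate tables allow**

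Let u be the proportion of subjects in an arm with at least one UU event (the overview) and g the proportion with at least one Grade 1 common reaction (the any-time category). I assume that category counts subjects with any such reaction. If it is given term by term, g itself is only bounded. The overlap of the two groups of subjects is not reported, so:

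- all-TE-AE rate: at least max(g, u), at most min(1, g + u);
- if the two are independent: 1 − (1 − g)(1 − u);
- shortfall of the overview under independence: g(1 − u).

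For related events even g is missing, because the common-event table is not described as split by relatedness. The most that can be said is that the all-related rate lies between the UU related rate and that rate plus g.

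**Illustration**

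The values of g and u are assumptions. The 20 subjects per arm is the Part B completion target.

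| g | u (overview) | All TE-AEs, independent | Bounds |
|---|---|---|---|
| 10% | 30% (6/20) | 1 − 0.9 × 0.7 = 37% | 30–40% |
| 30% | 30% (6/20) | 1 − 0.7 × 0.7 = 51% | 30–60% |
| 50% | 30% (6/20) | 1 − 0.5 × 0.7 = 65% | 50–80% |

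With g and u each between 10% and 50%, the overview falls short by 5 points (0.10 × 0.50) to 45 points (0.50 × 0.90) under independence, and by 0 to 50 points over all possible overlaps.

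**Difference between arms**

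- Take u = 30% in both arms and g = 50% on OXE-103, 10% on placebo. The overview difference is 0 points. The all-TE-AE difference is 65 − 37 = 28 points under independence, and anywhere from 50 − 40 = 10 to 80 − 30 = 50 points from the bounds.
- Take instead g = 30% in both arms and u = 50% versus 30%. The overview difference is 20 points. The all-TE-AE difference is 65 − 51 = 14 points.

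The level within an arm can only be equal or too low. The difference between arms can be too small or too large. It is too small in the case of most interest, where mild common reactions are more frequent on the active drug.

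**The case against.** The strongest reply is that nothing is hidden. Common reactions have their own table by treatment group, with an any-time category. Those of Grade 2 or higher are in the overview, so only mild, expected events sit outside it. Read literally, the SOC/PT sentence covers every TE-AE and every related TE-AE, and the listing covers every TE-DAE. The disposition table shows why subjects stopped. The independent medical monitor receives all reported events after 10 and 30 subjects are enrolled, so oversight does not depend on the UU label. The study is a descriptive pilot, and no safety test or stopping rule uses these counts.

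Most of this stands. A reader might infer that mild common reactions vanish from the report, that the safety result as a whole is biased, or that Part B cannot be compared with placebo on all events. The documents support none of these. The events are tabulated elsewhere, all are collected, and the two tables bound the combined rate. Nor do the documents show that the excluded events will fall mainly on the OXE-103 arm: they give no rates by arm for this population.

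The reply does not restore the missing count. Two marginal tables do not give a subject-level total. The SOC/PT sentence follows directly on the UU overview, so its scope can be read either way. Even on the wide reading it promises counts by SOC and PT, without stating a row for subjects with any event.

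**Conclusion.** The point holds in a limited form. The overview in SAP 6.9 reports UU events only, and no planned overview gives the subject-level incidence of all TE-AEs, all related TE-AEs or all TE-DAEs. Read alone, it can understate these incidences and the Part B difference. The amount cannot be estimated from the documents, and the percentages above show only what is possible under assumed rates.

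The conclusion rests on reading the UU limit as applying to every row of the overview, which is what both 5.4 and 6.9 say. It does not depend on how the SOC/PT and listing sentences are read. If those cover all TE-AEs, discontinuations are fully traceable and related events appear by term, but the overview remains incomplete. For a descriptive pilot this is a reporting defect of low to moderate weight. It deserves correction because it changes the headline safety figures and the data are already collected.

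**What to change.** In SAP 5.4 and 6.9, define the overview for all TE-AEs: any, serious, related, leading to discontinuation, and Grade 2 or higher. Show UU and common Grade 1 events as sub-rows, so the present split is kept. State that the SOC/PT tables and the TE-SAE and TE-DAE listings include all TE-AEs. Because the sub-rows depend on which reactions are called common, and the SAP does not list them, name the terms or cite their source.

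Make the change before Part B is unblinded, so that the combined rows are pre-specified. The cost is some wording and a few table rows, with no new data collection. The one real downside for the sponsor is that headline adverse-event rates may look less favourable.
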